## 7.5. Dose Modification

Guidelines for dose interruption or drug discontinuation are provided in Table 8. Decisions regarding dose interruptions or modifications will be made by the Investigator in consultation with the study medical monitor as needed based on the clinical evaluation of the participant. The Medical Monitor should be notified of all dose modifications within 72 hours.

All instances of study drug modification (dose interruption or discontinuation) should be documented in the participants' medical record and recorded in the eCRF. If the condition/event leading to the dose modification has resolved, the original dose level should be resumed, unless in the judgment of the Investigator this cannot be done safely.

**Table 8. Dose Modification Guidelines for Study Drug-Related Adverse Events**

Dose Interruption	
Event	Recommended Action
Grade 3 or higher AE that is (1) study -drug related in the opinion of the Investigator AND (2) that precludes continued dosing at the current dose level due to safety concern or lack of tolerability (in the Investigator's judgment)	Study Drug: May be held for 10 days. If, in the opinion of the Investigator, a Grade 3 AE has resolved to $\leq$ Grade 1, participant may resume daily dosing of study drug at a lower dose (not lower than 100 mg) or continue with the original dose or a lower daily dose.  Maximum dose hold is 28 continuous days. If, in the opinion of the Investigator, a longer dose hold is clinically needed, the Medical Monitor should be consulted.
ALT $\geq 3X$ ULN if ALT WNL at baseline OR $>3X$ ULN AND a $\geq 2$ -fold increase above baseline values if elevated ALT values at baseline  In the absence of additional signs of compromised liver function such as elevated PT, aPTT, INR, elevated conjugated bilirubin, jaundice, or hepatic pain.	Study drug: Confirm by repeat testing within 48 to 72 hours if possible and then repeat liver panel at least weekly until ALT levels improve.  Additional Actions: If ALT levels continue to increase hold the study drug for 10 days and notify the Medical Monitor.  Upon resolution of the elevated ALT, the participant may resume daily dosing of study drug at the original dose or a lower dose.
ALT $\geq 5X$ and $<8X$ ULN (confirmed by repeat testing within 48 to 72 hours)  In the absence of additional signs of compromised liver function such as elevated PT, aPTT, INR, elevated conjugated bilirubin, jaundice, or hepatic pain.	Study drug: Hold the study drug for 10 days.

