**Table 8. Dose Modification Guidelines for Study Drug-Related Adverse Events**

	
Additional actions: Repeat liver panel test within 48 to 72 hours if possible and then at least weekly until resolution to <math><5X</math> ULN, with continued monitoring thereafter. If ALT continues to increase within 1 week after the medication is restarted, treatment should be interrupted, and the Medical Monitor should be notified.
 
Upon resolution of the elevated ALT, the participant may resume daily dosing of study drug at the original dose or a lower dose.

Drug Discontinuation	
Event	Recommended Action
Grade 3 or Higher Study Drug-Related SAE	
Study Drug: Discontinue study drug. If the Investigator considers that the participant would benefit from continuing treatment, the Medical Monitor should be contacted for discussion.

Consider treatment discontinuation if:
 
 
ALT <math>>8X \times</math> ULN
 
ALT <math>>3X</math> ULN with additional signs of compromised liver function such as elevated PT, aPTT, INR, elevated conjugated bilirubin, jaundice, or hepatic pain, appearance of fatigue, nausea, vomiting, right upper quadrant pain or tenderness, fever, rash, and/or eosinophilia
 
	
Study drug: Hold dose.
 
Additional actions: Sponsor recommends confirmation by repeat testing within 48 to 72 hours and assess potential reversible causes of liver function test abnormalities. Contact the Medical Monitor for discussion of study drug discontinuation.

Abbreviations: AE, adverse event; ALT, Alanine aminotransferase; aPTT, activated partial thromboplastin time; INR, international normalized ratio; PT, prothrombin time; SAE, serious adverse event; ULN, upper limit of normal; WNL, within normal limits.

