- Participants with AST/ALT and T bili baseline values within the normal range who subsequently present with AST OR ALT values  $\geq 3 \times \text{ULN}$  AND a T bili value  $\geq 2 \times \text{ULN}$  with no evidence of hemolysis and an alkaline phosphatase value  $< 2 \times \text{ULN}$  or not available.
- For participants with baseline AST OR ALT OR T bili values above the ULN, the following threshold values are used in the definition mentioned above, as needed, depending on which values are above the ULN at baseline:
  - Preexisting AST or ALT baseline values above the normal range: AST or ALT values  $\geq 2$  times the baseline values AND  $\geq 3 \times \text{ULN}$ ; or  $\geq 8 \times \text{ULN}$  (whichever is smaller).
  - Preexisting values of T bili above the normal range: T bili level increased from baseline value by an amount of  $\geq 1 \times \text{ULN}$  or if the value reaches  $\geq 3 \times \text{ULN}$  (whichever is smaller).

Because knowledge of the total and unconjugated bilirubin, may suggest the treatment assignment, these measurements will be redacted to the Investigator and monitored on a

regular basis by an unblinded team. Rises in AST/ALT and T bili separated by more than a few weeks should be assessed individually based on clinical judgment; any case where uncertainty remains as to whether it represents a potential Hy's law case should be reviewed with the sponsor.

The participant should return to the investigator site and be evaluated as soon as possible, preferably within 48 hours from awareness of the abnormal results. This evaluation should include laboratory tests, detailed history, and physical assessment.

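### Table 8 leaves ALT of exactly 8x ULN, without other liver signs, between the 10-day hold row and the consider-discontinuation row

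*Protocol*

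**What the plan says.** Protocol Section 7.5, Table 8, has three rows that grade ALT elevation when no other sign of compromised liver function is present.

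- **Retest row.** Entry is ALT at least 3x ULN if baseline was normal, or above 3x ULN with at least a 2-fold increase if baseline was elevated. There is no upper limit. The action is a repeat within 48 to 72 hours if possible and a liver panel at least weekly. A hold is conditional: "If ALT levels continue to increase hold the study drug for 10 days and notify the Medical Monitor".
- **Hold row.** Entry is ALT at least 5x and below 8x ULN, "confirmed by repeat testing within 48 to 72 hours". The action is a 10-day hold, whatever the trend.
- **Consider-discontinuation row.** This opens with "Consider treatment discontinuation if" and lists ALT above 8x ULN, or above 3x ULN with additional liver signs. The action is to hold the dose, repeat the test and discuss discontinuation with the Medical Monitor.

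A separate row covers a Grade 3 or higher drug-related SAE: "Discontinue study drug. If the Investigator considers that the participant would benefit from continuing treatment, the Medical Monitor should be contacted for discussion".

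Section 7.5 leaves these decisions to the Investigator, who consults the medical monitor as needed.

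**The concern.** The upper limit of the hold row and the lower limit of the consider-discontinuation row are both strict, so the value where they meet belongs to neither. It drops back to the mildest ALT action, or to none, while values just below and just above it are held. No clinical reasoning would make the middle value the least protected, so this looks like a drafting slip. At stake is whether a participant with a stable ALT of 8x ULN keeps taking study drug where the rest of the table would interrupt it.

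**Working it through.** **Inputs.** All thresholds come from Table 8; the plan gives no calculated figure to reproduce. Let x = ALT/ULN and b = baseline ALT/ULN, with no other liver signs. The 2-fold condition is read as x ≥ 2b.

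**Rules.**

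- Retest: x ≥ 3 if b ≤ 1; otherwise x > 3 and x ≥ 2b.
- Hold: 5 ≤ x < 8, confirmed.
- Consider discontinuation: x > 8.

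**Rows met, for confirmed values and assumed baselines.**

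| b | 2b | x = 7.9 | x = 8.0 | x = 8.1 |
|---|---|---|---|---|
| 1 | not needed | retest, hold | retest only | retest, discontinuation |
| 3.5 | 7.0 | retest, hold | retest only | retest, discontinuation |
| 4 | 8.0 | hold | retest only | retest, discontinuation |
| 4.1 | 8.2 | hold | none | discontinuation |

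The retest row stops catching x = 8 once 2b > 8, that is b > 4. For example, 8/4.1 = 1.95-fold. The documents do not say whether any participant has such a baseline. If the 2-fold condition were instead read as a rise of twice the baseline (x ≥ 3b), this limit would fall to 8/3 = 2.67. The gap at x = 8 is the same on either reading.

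**What a repeat test does after a first value of 8.0, for b ≤ 4.**

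- Repeat above 8: the consider-discontinuation row applies and the dose is held.
- Repeat from 5 to below 8: the hold row applies, if the repeat is taken as the confirmation.
- Repeat below 5: ALT is improving and no outright hold is intended.
- Repeat of exactly 8.0: still the retest row only, with no hold.

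So for b ≤ 4 the weaker action persists only if the second value also falls on the boundary.

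**After the change.** With the last rule set to x ≥ 8, the value 8.0 meets the consider-discontinuation row at all four baselines in the table.

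**The case against.** The strongest reply is that other provisions nearly always cover the case. Appendix 2 (Section 11.4.1) treats ALT above 4x ULN with no other explanation as potential DILI, to be reported as an SAE. If that SAE is drug-related and Grade 3 or higher, Table 8 says to discontinue. The Grade 3 AE row also permits a hold and has no ALT ceiling. Section 11.4.2 asks for closer monitoring above 3x ULN. Table 8 is titled for drug-related events and gives recommended actions, so an Investigator facing a stable 8x is free to hold.

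Most of this stands, and it is why the point is small. It does not remove the gap. The DILI text governs reporting and follow-up, not holding the dose, and the discontinuation rule depends on grade and on attribution to the drug. The protocol does not reproduce the ALT grade limits, so it cannot be shown from the documents that 8x ULN always meets that rule.

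A reader might be tempted by three stronger readings, which the documents do not support.

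- **That Appendix 2 contradicts Table 8.** The line beginning "Preexisting AST or ALT baseline values above the normal range: AST or ALT values" does include an inclusive 8x ULN. There it is one arm of a whichever-is-smaller rule within a Hy's law definition that also requires raised bilirubin. It serves a different purpose and is not a direct inconsistency.
- **That the overlapping ALT rows conflict.** A confirmed, stable value between 5x and 8x can literally meet both the retest and the hold row. But confirmation is the entry condition of the hold row, so the rows read naturally as steps.
- **That the table allows adult dosing below 100 mg.** The Grade 3 AE row says "at a lower dose (not lower than 100 mg) or continue with the original dose or a lower daily dose", and the ALT rows say "participant may resume daily dosing of study drug at the original dose or a lower dose". The wording is loose, but Tables 7 and 13 show 100 mg as the lowest adult dose. The 25 mg tablets are needed to make 150 mg (100 + 2 × 25).

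**Conclusion.** The point holds as a minor boundary error in a safety rule. ALT of exactly 8x ULN without other liver signs is excluded from both hold rows and receives a weaker action than 7.9x or 8.1x: retest only for baseline ALT up to 4x ULN, and no ALT-specific row above that.

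Its size is one value on the ALT scale, usually settled by the repeat test. It would be wrong to infer that 8x ULN is generally unmonitored, since the open-ended retest row catches it for any baseline up to 4x ULN. No endpoint, estimate or planned analysis depends on it.

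The conclusion assumes that the two inequality signs are printed as they read in the available text. The cell for above 8x carries a doubled multiplication sign, so the sign there is worth checking against the published table.

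**What to change.** In the consider-discontinuation row of Table 8, change ALT above 8x ULN to ALT at or above 8x ULN. This closes the gap without touching the other rows and adds no procedures. It helps only while participants are being dosed, or if the table is reused in another protocol. The SAP of June 2025 describes enrolment in the past tense, and the documents do not say whether dosing continues.

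The retest row should stay uncapped. Ending it at 5x would leave an unconfirmed first value of, say, 6x in no ALT-specific row, because the hold row requires confirmation.

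If the table is being edited anyway, two clarifications are optional: a sentence stating that the higher row governs once its condition is met, and a single statement that adult dose reductions do not go below 100 mg. Neither corrects an error.

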**Table 8. Dose Modification Guidelines for Study Drug-Related Adverse Events**

	
Additional actions: Repeat liver panel test within 48 to 72 hours if possible and then at least weekly until resolution to <math><5X</math> ULN, with continued monitoring thereafter. If ALT continues to increase within 1 week after the medication is restarted, treatment should be interrupted, and the Medical Monitor should be notified.
 
Upon resolution of the elevated ALT, the participant may resume daily dosing of study drug at the original dose or a lower dose.

Drug Discontinuation	
Event	Recommended Action
Grade 3 or Higher Study Drug-Related SAE	
Study Drug: Discontinue study drug. If the Investigator considers that the participant would benefit from continuing treatment, the Medical Monitor should be contacted for discussion.

Consider treatment discontinuation if:
 
 
ALT <math>>8X \times</math> ULN
 
ALT <math>>3X</math> ULN with additional signs of compromised liver function such as elevated PT, aPTT, INR, elevated conjugated bilirubin, jaundice, or hepatic pain, appearance of fatigue, nausea, vomiting, right upper quadrant pain or tenderness, fever, rash, and/or eosinophilia
 
	
Study drug: Hold dose.
 
Additional actions: Sponsor recommends confirmation by repeat testing within 48 to 72 hours and assess potential reversible causes of liver function test abnormalities. Contact the Medical Monitor for discussion of study drug discontinuation.

Abbreviations: AE, adverse event; ALT, Alanine aminotransferase; aPTT, activated partial thromboplastin time; INR, international normalized ratio; PT, prothrombin time; SAE, serious adverse event; ULN, upper limit of normal; WNL, within normal limits.

#### 7.5.1. Individual Level Stopping Rules for Participants Enrolling in C5351005 from the 200 mg Treatment Arm from Part A of C5351004

Continued dosing of the respective individual at the 200 mg dose level may be paused for review if any of the following occurs:

- If a participant reaches the ULN for Hb or hematocrit (based on local laboratory reference ranges for gender) and a Grade 2 or higher severity TEAE that is related to osivelotor.
- If a participant has signs of impaired tissue offloading of oxygen (new or increased from baseline headache, dizziness, fatigue).

## 7.6. Treatment of Overdose

For this study, any dose of osivelotor greater than the protocol defined dose of study intervention within a 24-hour time period will be considered an overdose. Based on the mechanism of action of osivelotor, an extreme overdose might decrease oxygen delivery to tissues. Transfusion, exchange transfusion, and/or hyperbaric oxygen therapy may be considered in the event of a medical emergency due to a suspected osivelotor overdose.

The Investigator will discuss the risks and concerns of investigational agent exposure with the participant/parent/legal guardian/legally authorized representative.

Participant/parent/legal guardian/legally authorized representative are to be instructed to contact their study site immediately if an overdose of study drug is suspected.

If a participant takes more than the protocol-defined dose of study drug in a day and experiences a drug related AE/SAE, this will be reported as an overdose (AEs/SAEs must be recorded on the AE eCRF and SAEs reported to Pfizer Safety) and a protocol deviation. However, if the participant did not experience any AEs/SAEs, this will only be reported as a protocol deviation. An overdose with AEs must be followed until any adverse effects are resolved or stabilized, or until reasonable attempts to determine resolution of the event are exhausted.

In the event of an overdose, the Investigator/treating physician should:

1. Contact the study medical monitor within 24 hours.
2. Closely monitor the participant for any AE/SAE and laboratory abnormalities as medically appropriate and follow up until resolution, stabilization, the event is otherwise explained, or the participant is lost to follow-up.
3. Document the quantity of the excess dose as well as the duration of the overdose in the CRF.
4. Overdose is reportable to Pfizer Safety **only when associated with an SAE**.
5. Obtain a blood sample for PK analysis within 1 day from the date of the last dose of study drug intervention if requested by the medical monitor (determined on a case-by-case basis).

Decisions regarding dose interruptions or modifications will be made by the Investigator in consultation with the study medical monitor as needed based on the clinical evaluation of the participant.

## 7.7. Concomitant Medications and Procedures

Study participants will be allowed to take other medications as needed except for those described in Section 11.6. Vaccines are allowed during the study. All concomitant medications will be documented.

In the interests of participant safety and acceptable standards of medical care, the Investigator will be permitted to prescribe treatment(s) at their discretion. Treatment with stable doses of

HU, L-glutamine are allowed. However, initiation of new SOC agents (eg, crizanlizumab and voxelotor) during treatment is strongly discouraged. All other standard therapeutic interventions for SCD and its complications (eg, hydration, analgesia, acute transfusions) are allowed under this protocol.

All concomitant treatments and/or procedures must be recorded in the participants' eCRF (procedure, medication, dose, treatment duration and indication).

#### **7.7.1. Healthcare Resource Utilization for Participants Enrolling from C5351004 Part B**

Healthcare resource utilization data (eg, hospitalizations, non-protocol specified medical visits, etc.) will be collected for all randomized participants. Specifically, healthcare resource utilization is evaluated based on the number of medical care encounters such as hospital admissions and their duration, outpatient visits, diagnostic tests and procedures, concomitant medications, and reasons for the encounters. This data will be self-reported by participants at the frequency described in the schedule of assessments. Participants should recall any hospitalizations or non-protocol required healthcare visits (ie, participant seeking medical attention for any reason) that occurred between visits. This data may also be obtained through electronic sources such as electronic medical records, where available.

### **8. DISCONTINUATION OF STUDY TREATMENT AND PARTICIPANT DISCONTINUATION/WITHDRAWAL**

Discontinuation of specific sites or of the study are detailed in Section 11.1.8.

#### **8.1. Early Discontinuation of the Study**

The Sponsor has the right to terminate this study at any time. Reasons for terminating the study may include, but are not limited to, the incidence or severity of AEs in this study or other studies with osivelotor indicating a potential health risk to participants.

In the instance of early termination of the study, the Sponsor will notify, in writing, the Investigators, regulatory authorities, and Institutional Review Boards/Independent Ethics Committees (IRBs/IECs) and will specify the reasons(s) for the termination.

#### **8.2. Discontinuation of Study Treatment**

Participants will be discontinued from study drug for any of the following reasons:

- Participant is lost to follow-up.
- A participant that does not take the full loading dose assigned may be discontinued following a discussion with the Medical Monitor.
- At the discretion of the Investigator.
- Participant is noncompliant.
- Pregnancy.
- Withdrawal of consent (participants are free to discontinue treatment or withdraw from the study at any time and for any reason. The Investigator must withdraw participants from the study who request to be withdrawn). Additionally, parent/legal

guardian/legally authorized representative can withdraw consent at any time and for any reason.

Participants should return to the study site for an EOS visit approximately 12 weeks after the last dose of study drug per the Schedule of Assessments (SoA) and Procedures (Section 2.1).

### 8.2.1. Potential Cases of Acute Kidney Injury

Participants exposed to IMP demonstrating transient or sustained increase in Screat (with decrease in Screat-based eGFR or eCrCl) require expedited evaluation to differentiate AKI from DICI. DICI is defined as transporter-mediated effect related to altered renal tubular creatinine handling without histological injury.

*AKI may be due to one or more types of injury, including DIKI. Differentiation of DIKI from other causes of AKI and from DICI may require clinical, radiographic, histopathologic, and laboratory assessments, as well as nephrology consultation.*

### Follow-Up Assessments

The participant should return to the site for evaluation as soon as possible, preferably within 48 hours of awareness of the abnormal results.

Evaluation should include physical examination, laboratory tests, detailed medical and surgical history, review of all medications (including recreational drugs and supplements [herbal]), family history, sexual history, travel history, blood transfusion, and potential occupational exposure to chemicals.

Laboratory assessments should include simultaneous serum cystatin C (Scys) and serum creatinine (Screat) tests. Estimates of eGFR, eCrCl and Screat-based eGFR and combined Screat-Scys-based eGFR should also be derived using the appropriate equation described in Section 11.5.

Assessments of urine albumin-to-creatinine ratio or urine volume may also be performed as appropriate.

If appropriate, nephrology consultation may be recommended to facilitate differentiation of renal parenchymal disease, pre-renal azotemia, and post-renal obstruction.

### Differentiating Acute Kidney Injury from DICI

A confirmed Screat increase is defined as:

- (i)  $\geq 0.3$  mg/dL ( $\geq 26.5$   $\mu$ mol/L) within 48 hours OR
- (ii) confirmed Screat increase  $\geq 1.5$  times baseline (known or suspected to have occurred within the prior 7 days).

Based on the assessments performed, suspected AKI (including DIKI) may be differentiated from DICI as follows.

### Pediatric Participants

	AKI (including DIKI) Any one of the below	DICI
Scys & Screat	Simultaneous, confirmed Scys increase and confirmed Screat increase	Confirmed Screat increase without confirmed increase in reflex Scys
Albuminuria	Confirmed albuminuria increase (see Section 11.5 for Grades A1 to A3 quantitation)	
Urine volume	Urine volume <0.5 mL/kg/h for 6 consecutive hours	

### Adult Participants

	AKI (including DIKI) Any one of the below	DICI
Scys & Screat	Simultaneous, confirmed serum cystatin C (Scys) increase and confirmed Screat increase	Confirmed Screat increase without confirmed increase in reflex Scys AND
eGFR	Decrease in Screat-based eGFR and combined Screat-Scys-based eGFR (when available)	Confirmed Screat-based eGFR decrease without confirmed combined Screat-Scys-based eGFR decrease.
Albuminuria or proteinuria	Confirmed albuminuria increase (see Section 11.5 for Grades A1 to A3 quantitation)	
Urine volume	Urine volume <0.5 mL/kg/h for 6 consecutive hours	

Regardless of the presence or absence of increase in Screat, DIKI and other causes of AKI may be suspected if either (i) new-onset or worsening albuminuria or proteinuria are detected or (ii) urine volume (if measured) is <0.5 mL/kg/h for 6 consecutive hours.

All confirmed cases of clinically relevant decrease in kidney function should be considered potential cases of DIKI if no other reason for the kidney function abnormalities has been found.

See [Appendix 2: Liver Safety: Suggested Actions and Follow-Up Assessments](#) for instructions for laboratory testing to monitor kidney function and reporting laboratory test abnormalities.

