## 11.5. Appendix 3: Kidney Safety Monitoring Guidelines

### 11.5.1. Laboratory Assessment of Change in Kidney Function and Detection of Kidney Injury

Standard kidney safety monitoring requires assessment of baseline and postbaseline Screat measurement to estimate kidney function [Screat-based eGFR] or creatinine clearance [eCrCl]. Baseline and postbaseline Scys makes it feasible to distinguish AKI from other causes of Screat increase. If Screat increase is confirmed after baseline, then reflex measurement of Scys is indicated.

**ADULTS:** Currently, 2021 CKD-EPI eGFR equations (Screat-only based and combined Screat plus Scys-based) are valid for use in adults only. At baseline Screat and Scys values are needed to calculate 2021 CKD-EPI eGFR by Screat-only based equation (see Table in Section 11.5.2.1) and by combined Screat plus Scys-based equation. When post-baseline Screat increase  $\geq 0.3$  mg/dL is confirmed, then reflex Scys measurement is needed to enable post-baseline comparison of eGFR changes (Screat-only based eGFR and combined Screat plus Scys eGFR).

**PEDIATRICS:** Currently, no Screat plus Scys eGFR equations have been universally adopted for pediatrics. Therefore, comparison of baseline Screat and Scys to post-baseline Screat and reflex Scys are utilized to support differentiation of AKI from DICI.

Regardless of whether kidney function monitoring tests are required as a routine safety monitoring procedure in the study, if the investigator or sponsor deems it necessary to further assess kidney safety and quantify kidney function, then these test results should be managed and followed per standard of care.

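### Adult AKI/DICI table: a creatinine rise with unchanged cystatin C always lowers combined eGFR, so read literally the defining DICI pattern meets an AKI row and fails the DICI eGFR condition

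*Protocol*

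**What the plan says.** Section 8.2.1 asks for expedited evaluation of any creatinine (Screat) rise in order to tell AKI from DICI. It defines DICI as a "transporter-mediated effect related to altered renal tubular creatinine handling without histological injury". A confirmed Screat increase is at least 0.3 mg/dL within 48 hours, or at least 1.5 times baseline. The tables that follow are introduced with "suspected AKI (including DIKI) may be differentiated from DICI as follows".

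In the adult table, one row is sufficient for AKI. The eGFR row of the AKI column reads "Decrease in Screat-based eGFR and combined Screat-Scys-based eGFR (when available"; it gives no size and does not say that the fall must be confirmed. The DICI column has two conditions joined by AND: a confirmed Screat increase without a confirmed cystatin C (Scys) increase, and "Confirmed Screat-based eGFR decrease without confirmed combined Screat-Scys-based eGFR decrease".

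The pediatric table has no eGFR row. Its DICI cell is only "Confirmed Screat increase without confirmed increase in reflex Scys".

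Section 11.5.1 says that for adults "reflex Scys measurement is needed to enable post-baseline comparison of eGFR changes", and Section 11.5.2.1 gives the equations. SAP Section 2.2.3 says that only participants from Part A of C5351004, all adults, were enrolled. The adult table is therefore the one in use.

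**The concern.** A change in tubular creatinine handling without injury shows up as Screat up and Scys unchanged. That is the pattern the table is there to recognise. Combined eGFR, however, is a function of both markers, so it cannot stay level when only one of them moves. The adult table treats a fall in combined eGFR as a sign of injury and its absence as a requirement for DICI. It therefore points the benign pattern toward AKI.

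What is at stake is how an investigator labels an event. Section 11.5.4 grades AKI only from Grade 3 upward, while a creatinine increase has its own term starting at Grade 1. The text below the adult table adds that "All confirmed cases of clinically relevant decrease in kidney function should be considered potential cases of DIKI" when no other reason is found, so a table that steers away from DICI also leans toward attributing the event to the drug.

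**Working it through.** **Inputs.** The equations are those of protocol Section 11.5.2.1, and the triggers are the two confirmed-increase rules of Section 8.2.1. In the combined equations the Screat exponents are −0.219 (female, Screat ≤0.7), −0.144 (male, ≤0.9) and −0.544 (either sex above those knots). The Scys exponents are −0.323 (≤0.8 mg/L) and −0.778 (>0.8 mg/L). The plan states no figure of its own on this point.

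**Step 1: direction.** With Scys and age fixed, their factors cancel:

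combined eGFR after / before = (Screat after / Screat before)^b, with b = −0.144, −0.219 or −0.544.

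Each equation is continuous at its knot and decreasing in Screat on both sides, so the ratio is below 1 for any rise. The Screat-only equations (exponents −0.241, −0.302 and −1.200) also fall. Both halves of the AKI eGFR row are then met.

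**Step 2: size for a 1.5-fold rise.**
- Smallest fall: 1.5^−0.144 = 0.943, a fall of 5.7%.
- Largest fall: 1.5^−0.544 = 0.802, a fall of 19.8%.
- A rise that crosses a knot lies between these. The bounds do not depend on age, Scys or baseline Screat.

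**Step 3: size for +0.3 mg/dL**, with baseline Screat assumed to be 0.4–1.2 mg/dL.
- Smallest: male, 0.6 to 0.9: (0.9/0.6)^−0.144 = 0.943, a fall of 5.7%.
- Largest: female, 0.7 to 1.0: (1.0/0.7)^−0.544 = 0.824, a fall of 17.6%.

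**Step 4: worked cases** (age 30, Scys unchanged).

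| Case | Screat-only eGFR | Combined eGFR |
|---|---|---|
| Male, Screat 0.6 to 0.9, Scys 0.8 | 133.2 to 117.8 (−11.5%) | 127.3 to 120.1 (−5.7%) |
| Male, Screat 0.9 to 1.2, Scys 0.8 | 117.8 to 83.4 (−29.2%) | 120.1 to 102.7 (−14.5%) |
| Female, Screat 0.7 to 1.0, Scys 0.8 | 118.7 to 77.3 (−34.8%) | 115.6 to 95.2 (−17.6%) |
| Male, Screat 1.0 to 1.5, Scys 1.0 | 103.8 to 63.8 (−38.5%) | 95.3 to 76.4 (−19.8%) |

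On a wide assumed grid (both sexes, age 30, Screat 0.30–3.00 mg/dL, Scys 0.4–3.0 mg/L, both triggers), combined eGFR fell in 5,940 of 5,940 cases.

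**Step 5: when DICI alone can be returned.** Measured Scys must fall enough to cancel the creatinine term. For a 1.5-fold rise:
- Least: 1 − exp(−0.144 × ln 1.5 / 0.778) = 7.2%.
- Most: 1 − exp(−0.544 × ln 1.5 / 0.323) = 49.5%.

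**Step 6: would a size for the eGFR fall repair the row?** Not cleanly. With Screat ×1.5 and Scys ×1.2, combined eGFR falls by 11.1% to 30.4% (Screat 0.4–1.2 mg/dL and Scys 0.6–1.1 mg/L assumed). This overlaps the 5.7% to 19.8% seen with unchanged Scys. Even with Scys ×1.5 the fall can be 17.3%: for a male with Screat staying at or below 0.9 and Scys going from 0.50 to 0.75, 1.5^−0.144 × 1.5^−0.323 = 0.827.

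**The case against.** **The word confirmed implies a meaningful size.** The DICI cell asks for no confirmed combined fall, and the text below the table speaks of clinically relevant decreases. But Section 8.2.1 gives a size only for Screat. The word confirmed is also absent from the AKI eGFR row, so reading a size into the DICI cell would put the case in both columns. If repeat samples confirm the Screat rise and Scys is unchanged on them, the combined fall is confirmed too.

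**The two eGFRs are meant to be compared.** They do differ: −29.2% against −14.5% in one case above. The row, however, asks only whether both fell, not by how much they differ.

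**The availability qualifier.** It covers a missing Scys, which is not the case described here.

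**A reader might infer that the table can never return DICI alone.** That goes too far. If Scys is measured with an assumed CV of 3%, 5% or 8% at each time point, truly unchanged Scys would still give no measured combined fall in about 4%, 14% or 25% of pairs. That holds in the most favourable stratum: male, Screat at or below 0.9 after the 1.5-fold rise, Scys above 0.8. In the −0.544 strata it is under 1%. The strict statement is limited to unchanged measured Scys.

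**It is only guidance, and no consequence is shown.** Most of this stands. Section 8.2.1 says the two may be differentiated, asks for a clinical work-up and allows nephrology consultation. Table 8 has no kidney dosing rule. Laboratory findings become adverse events on clinical significance (Section 9.4.7.2). This limits the consequence but does not repair the table.

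**Conclusion.** The point holds as an error in investigator safety guidance. For an adult with a confirmed Screat rise and unchanged Scys, combined eGFR must fall, by 5.7% to 19.8% for a 1.5-fold rise. The first range needs no assumption beyond unchanged Scys; the 5.7% to 17.6% range for +0.3 mg/dL rests on the assumed baseline Screat. Read literally, such a case meets an AKI row and fails a DICI condition. Nothing elsewhere in the protocol resolves the conflict. The pediatric table does not have it.

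The error is in the cautious direction. A reader might infer that the primary safety results are biased, but the documents do not support that. No SAP output uses the table directly: SAP Section 6.1.1 takes adverse events from the AE eCRF. An effect on TEAE counts could arise only through how an event is labelled, and the documents do not say how often such cases occur. Nor do the documents support any particular Scys cut-off; one would have to be chosen from assay data that they do not give.

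**What to change.** 1. Let the AKI eGFR row count only together with a confirmed Scys increase.
2. Remove the clause about the combined eGFR from the adult DICI cell, so that adult DICI rests on a Screat increase without a Scys increase, as in the pediatric table.
3. Send cases without both a baseline and a reflex Scys to the clinical work-up already described in Section 8.2.1, not to the table.
4. If an amendment is too late, state in the CSR, for any adult AKI case, whether it rested on the eGFR row alone.

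No size is given for a confirmed Scys increase either. Setting one with the central laboratory would help, but it is not needed to remove this conflict.

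**Cost.** A wording change to one table, by amendment or clarification letter, with no added visits. For the event sample, Section 8.2.1 already says "Laboratory assessments should include simultaneous serum cystatin C (Scys) and serum creatinine (Screat) tests". Baseline is less certain: Section 11.5.1 needs a baseline Scys, but the adult schedules (Tables 1 and 2) have no cystatin C row and Table 9 lists it only under other tests. How many adults have a baseline value is unknown. After the change the eGFR row adds little beyond the first AKI row, and more cases rest on clinical judgement. The SAP describes enrolment in the past tense, so only cases still to be assessed or reported would benefit.
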